#### **D. Original Statistical Analysis Plan**

The primary analysis will be an intention to treat analysis among randomized patients with confirmed COVID-19. The researchers seek to enroll at least 259 Black or Latino patients in each arm to achieve 90% power to detect a mean difference of 2 DOAH, assuming a type I error rate of 0.05. Given that Black and Latino patients comprise 61% of the COVID Watch sample, this indicates a target minimum sample size of at least 850 patients with confirmed COVID-19.

Linear mixed effects models will be used to assess the incremental effect of home pulse oximetry on DAOH relative to COVID Watch alone. Random intercepts will be used to account for clustering by testing site. Randomization will theoretically ensure balance of measured and unmeasured covariates between arms. Factors deemed to be associated with the outcome a priori will be adjusted for to increase efficiency. These include: age, sex, race, ethnicity, insurance, median income of residential ZIP code and ED vs. outpatient enrollment.

The researchers will examine heterogeneity in treatment effects using interaction terms by treatment comparator group and: the following (1) location of enrollment (outpatient vs ED); (2) primary care in the health system (yes or no); (3) insurance (none/Medicaid/Medicare/private); and (4) race/ethnicity, including an evaluation of Black and Latino patients separately. A sensitivity analysis will be performed to compare outcomes to UPHS COVID-19 patients not enrolled in COVID Watch using a propensity score analysis. The researchers will record and report all reasons for dropout and missing data, and account for all patients in reports. Because this research is being conducted in the context of routine care and COVID Watch requires a working cell phone, the researchers anticipate fewer losses to follow-up than is typical.

As secondary analyses, the researchers will repeat the above analyses in the full population of randomized patients now including the population of patients placed into COVID Watch who had suspected COVID-19 but ended up having negative COVID-19 tests.

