## E. Final Statistical Analysis Plan

The primary analysis will be an intention to treat analysis among randomized patients with confirmed COVID-19. The researchers seek to enroll at least 204 Black or Latino patients in each arm to achieve 90% power to detect a mean difference of 1 DOAH, assuming a type I error rate of 0.05. Given that Black and Latino patients comprise 61% of the COVID Watch sample, this indicates a target minimum sample size of at least 1078 patients with confirmed COVID-19.

As the primary analyses, the researchers will use an intention-to-treat approach. The researchers also performed a per protocol analysis including only those patients who actively participated on their allocated protocol (e.g., responded to at least one text-message check-in). For both analyses, the researchers compared mean DAOH between study groups using two-sample t-tests. Adjustment for covariates via regression was not deemed necessary as all sociodemographic and clinical characteristics were well balanced between arms. The researchers also compared continuous secondary outcomes including mean number of outpatient visits, emergency department encounters, and hospitalizations using t-tests. The researchers compared categorical secondary outcomes using Fisher's Exact test. A prespecified subgroup analysis was completed by comparing outcomes for Black and Hispanic patients to White patients. Exploratory subgroup analyses were conducted for age strata and enrollment context (inpatient, outpatient, and ED). All tests were two-sided and a p-value  $< 0.05$  was considered statistically significant in the primary analyses. In subgroup analyses, to account for multiple testing, Bonferroni corrected p-value cut-offs are provided for the results in the supplementary tables. All analyses were conducted using R statistical software version 3.6.0 (R Foundation for Statistical Computing, Vienna, Austria. URL <https://www.R-project.org/>).

[Below is from original SAP]

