Linear mixed effects models will be used to assess the incremental effect of home pulse oximetry on DAOH relative to COVID Watch alone. Random intercepts will be used to account for clustering by testing site. Randomization will theoretically ensure balance of measured and unmeasured covariates between arms. Factors deemed to be associated with the outcome a priori will be adjusted for to increase efficiency. These include: age, sex, race, ethnicity, insurance, median income of residential ZIP code and ED vs. outpatient enrollment.

The researchers will examine heterogeneity in treatment effects using interaction terms by treatment comparator group and: the following (1) location of enrollment (outpatient vs ED); (2) primary care in the health system (yes or no); (3) insurance (none/Medicaid/Medicare/private); and (4) race/ethnicity, including an evaluation of Black and Latino patients separately. A sensitivity analysis will be performed to compare outcomes to UPHS COVID-19 patients not enrolled in COVID Watch using a propensity score analysis. The researchers will record and report all reasons for dropout and missing data, and account for all patients in reports. Because this research is being conducted in the context of routine care and COVID Watch requires a working cell phone, the researchers anticipate fewer losses to follow-up than is typical.

As secondary analyses, the researchers will repeat the above analyses in the full population of randomized patients now including the population of patients placed into COVID Watch who had suspected COVID-19 but ended up having negative COVID-19 tests.

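### The final SAP replaces the prespecified covariate-adjusted model for DAOH with a t-test because the arms were seen to be balanced, and Section F neither describes nor dates the switch

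*Combined protocol and SAP*

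**What the plan says.** Section D (original SAP) names a linear mixed effects model for DAOH. On clustering it says: "Random intercepts will be used to account for clustering by testing site". On covariates it says: "Factors deemed to be associated with the outcome a priori will be adjusted for to increase efficiency". The list is age, sex, race, ethnicity, insurance, median income of the home ZIP code, and ED versus outpatient enrolment. The same paragraph notes that randomisation should in theory balance the covariates, and adjusts all the same.

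Section E (final SAP), on the intention-to-treat and per-protocol analyses, says: "For both analyses, the researchers compared mean DAOH between study groups using two-sample t-tests". The reason for not adjusting is: "Adjustment for covariates via regression was not deemed necessary as all sociodemographic and clinical characteristics were well balanced between arms". No reason is given for losing the site intercepts.

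Section E then prints a bracketed label, "Below is from original SAP", and repeats the earlier text in the future tense, including "Linear mixed effects models will be used to assess the incremental effect of home pulse oximetry on DAOH relative to COVID Watch alone" and "A sensitivity analysis will be performed to compare outcomes to UPHS COVID-19 patients not enrolled in COVID Watch using a propensity score analysis". The label gives the origin of that text, not its standing.

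Section F announces three modifications, all made before outcomes were ascertained. Its prose and its table give two: the Bonferroni clarification (11/02/20) and the larger sample size (12/17/20). The protocol's own amendment summary (Section C) does not mention the change of model.

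**The concern.** The primary model was changed, and the only reason on record could be known only after patients had been randomised and the arms compared at baseline. A rule of adjusting only if the arms look unbalanced makes the primary analysis depend on by-arm data. Prespecification is meant to prevent that.

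The reason also misses its target. The original SAP adjusted for efficiency while already expecting balance, so finding balance is no new argument against adjusting. It has no bearing on clustering by testing site.

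Because Section F neither describes nor dates the switch, a reader cannot place it relative to access to by-arm data or to outcomes. Nor can a reader tell whether the reprinted analyses that Section E does not replace are still planned. These are the primary-care and insurance interactions, the propensity-score comparison, and the analysis of all randomised patients including those who tested negative.

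**Working it through.** **Texts side by side**

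| Item | Original SAP (D) | Final SAP (E), operative text | Section F |
|---|---|---|---|
| DAOH model | Linear mixed model | Two-sample t-test | Not mentioned |
| Covariates | Seven listed factors, for efficiency | None, because arms balanced | Not mentioned |
| Site intercepts | Yes | Absent, no reason | Not mentioned |
| Modifications | – | – | Three counted, two described and dated |

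**Timing.** Final Protocol 5.3 plans recruitment to about March 1, 2021. The last dated entry in Section F is 12/17/20. If recruitment ran as planned, balance of the complete arms could not have been known on that date. The decision may still have been earlier than the wording; the documents do not say.

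**The plan's own figures.** The original total reproduces: 2 × 259 / 0.61 = 849.2, so 850. The final one does not: 2 × 204 / 0.61 = 668.9, so 669, not 1078. That is a separate matter and nothing here depends on it. Both 204 and 539 per arm (1078 / 2) are used below.

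**Precision**

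- SD of DAOH: not stated. Solving a two-sample t-test for 204 per arm, a 1-day difference, 90% power and two-sided 0.05 gives 3.11 (normal approximation 3.12). It is a Black or Latino target, applied here to all patients.
- Covariate parameters k: age 1, sex 1, race 1-2, ethnicity 1, insurance 3, ZIP income 1, enrolment 1-2, so 9 to 11.
- R² (share of DAOH variance explained by the covariates): not in the documents, so 1% to 20% is shown.
- Site intercepts are not modelled.

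Ratio of 95% CI widths, adjusted over unadjusted, averaged over chance imbalance, with N the total:

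ratio = [t(0.975, N−2−k) / t(0.975, N−2)] × √[(1−R²)(N−3)/(N−k−3)]

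Example, N = 408, k = 9, R² = 1%: 1.00007 × √(0.99 × 405/396) = 1.0063, or 0.6% wider.

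| R² | 204 per arm (k = 9 / 11) | 539 per arm (k = 9 / 11) |
|---|---|---|
| 1% | 1.0063 / 1.0089 | 0.9992 / 1.0001 |
| 5% | 0.9858 / 0.9883 | 0.9788 / 0.9797 |
| 20% | 0.9046 / 0.9069 | 0.8982 / 0.8990 |

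At 204 per arm, power for 1 day goes from 90% unadjusted to 89.5%-89.6% at R² 1% and to 94.7%-94.8% at R² 20%. At 539 per arm, unadjusted power is already 99.95%. Break-even R² is 2.2%-2.7% at 204 per arm and 0.8%-1.0% at 539.

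**With exactly balanced arms.** The factor (N−3)/(N−k−3) is the average price of chance imbalance. If balance is exact, it drops out. At N = 408 and R² 1% the ratio is then 1.0001 × √0.99 = 0.995, about 0.5% narrower, and break-even R² falls to about 0.014%-0.017%. In that same case the t-test is conservative: its true two-sided error is 2[1 − Φ(1.96/√(1−R²))], which is 4.4% at R² 5% and 2.8% at R² 20%. Observed balance therefore strengthens the efficiency case for adjusting.

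**The case against.** The best defence has five parts.

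- **Validity.** The t-test is valid under randomisation, and the stated reason cites baseline characteristics, not outcomes. This stands. A reader might infer from the past-tense wording that the model was chosen after seeing results. The documents do not support that: the wording shows knowledge of baseline data by arm and nothing more.
- **Timing statement.** Section F says that every modification preceded outcome ascertainment and counts one more than it lists. The switch may be that third item, in which case the log lacks a line. This stands as a possibility. Without a description or date, the general statement cannot be tied to the switch.
- **Status of the reprint.** A reader might infer that Section E contains two competing primary models. The more natural reading is that the t-test is operative and the mixed model is reprinted for reference. Real uncertainty remains only for the analyses that Section E does not replace.
- **Enrolment context.** The reprinted two-level enrolment variable omits patients enrolled at hospital discharge. The operative text already uses three levels: "Exploratory subgroup analyses were conducted for age strata and enrollment context (inpatient, outpatient, and ED". The two-level version matters only if the reprinted model is revived as written.
- **Remedy.** If outcomes have already been analysed, going back to the adjusted model is itself a further change of primary analysis. This stands and must be disclosed.

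Instability of site intercepts is also a fair worry. The documents neither define testing site nor give the number of sites, so its extent cannot be computed.

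**Conclusion.** The point holds and should be fixed. A prespecified, covariate-adjusted primary model was replaced by an unadjusted test for a reason that depends on by-arm data, answers neither the efficiency rationale nor the clustering term, and is not described or dated in the amendment summary. The damage is to prespecification and to the reader's ability to follow the plan. It is not a finding of bias, of an invalid test or of a choice made on results.

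The effect on precision is uncertain and may be small. It depends on the assumed R² and on whether chance imbalance is averaged over; the power figures rest on the back-solved SD. A reader might infer a material loss of power. At the stated 1078 patients the figures do not support that for a 1-day difference. The main gain from the fix is a primary model that does not depend on observed balance.

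**What to change.** - Make the DAOH model adjusted for the covariates listed in Section D the primary intention-to-treat analysis, whatever balance is observed, with enrolment context at the three levels that Section E already uses. Label the third level as a change from the original SAP.
- Report the two-sample t-test beside it as a labelled sensitivity analysis.
- Delete observed balance as the reason for not adjusting.
- In Section F, log and date the switch to the t-test and any return to the adjusted model, each relative to access to by-arm data and to outcomes. Say whether the switch is the third modification.
- Say whether the testing-site intercepts are kept and, if not, why.
- State which reprinted analyses remain in force: primary-care and insurance interactions, propensity-score comparison, full randomised population.

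The cost is SAP wording, a few log lines and one extra model. Adjustment uses 9 to 11 degrees of freedom. If the covariates are weakly prognostic, the interval could be slightly wider: on average up to 0.9% at 204 per arm with R² 1%, and not at all at that R² if the arms are exactly balanced. If outcomes have already been analysed, the return to the adjusted model must be reported as a post hoc change, with both results shown.

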### 3. Aims

**3.1 Primary outcome.** The primary outcome measure is the difference in Days Alive and Out of Hospital.

**3.2 Secondary outcomes.** The secondary outcome measure is the difference self-reported anxiety on a single question adapted from the Emotional Distress-Anxiety Short Form 4a scale on day 0, 7, and 14 after enrolment in COVID Watch.

**3.3 Exploratory outcomes.** The researchers will explore several other outcomes of interest. These included differences in: 1) 30-day mortality; 2) incidence and timing of remote monitoring escalations to nursing care and subsequent emergency department referrals; 3) health care utilization including outpatient, emergency department, inpatient, and ICU care; 4) self-perceptions of feeling safe at managing illness; and 5) rates of discordance between dyspnea symptoms and hypoxia as measured on home pulse oximetry.

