## 8.2 Procedures

1. Patients are started on COVID Watch as routine care based on confirmed or clinical suspicion for COVID-19 via the integration of the Way To Health (W2H) platform with the electronic health record.
2. Patient receives a text message to proceed in COVID Watch as is current routine care.
3. For this study, W2H auto-generates and sends the study's Research Coordinator (RC) a daily excel report with a list of new COVID Watch enrollees at regular intervals (e.g., every 2 hours). The report includes the randomized arm assignment (COVID Watch or COVID Watch + Pulse Oximetry), along with the patient's phone number.
4. The RC alerts patients randomized to COVID Watch + Pulse Oximetry via phone call and/or text message that there will be a next day pulse ox device delivery and that once received, the patient will start to measure and report their oxygen levels. The RC confirms the patient's mailing address and instructs patients that in the meantime, they should continue to respond to COVID Watch check-ins per standard protocol. The patient is instructed to text or call once they have received the pulse oximetry device. If language preference is Spanish, an interpreter is required on the call.

- i. If the patient cannot be reached by text, the RC calls and if necessary, leaves a voicemail and the patient will still be sent a pulse ox.
- 5. The RC sends a pulse oximetry device via UPS 11am and 5pm. The package will include a pulse oximetry device (with barcode), printed patient instructions in the appropriate language, and prepaid, labeled return envelope to be used at the end of their COVID Watch enrollment
- 6. The RC logs device identifier, date and time of drop off of package for each patient
- 7. The RC tracks device receipt (via both UPS tracking and/or patient self-report) and contacts the patient via text and/or phone call to ensure the patient understands how to use the device. If language preference is Spanish, an interpreter is required on the call.
- 8. The RC changes patient protocol from COVID Watch to COVID Watch + Pulse Oximetry.
- 9. The RC follows up with patients via text and/or phone call in the event that the device is not returned within 2 weeks of being discharged from COVID Watch

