### **9.5.1 Research Materials and Maintenance of Data Security**

The study involves data collected with protection of confidentiality. Study and survey data collected during the baseline and subsequent visits will be kept electronically secure as described in the Data confidentiality above. No one but the PI, project manager, and study staff responsible for the follow up will have access to these files. Any data used for results will only be presented in a de-identified manner in the aggregate.

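### The final SAP never names the protocol's only secondary outcome, anxiety at days 0, 7 and 14, and its generic rule does not use day 0 as a baseline

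*Combined protocol and SAP*

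**What the plan says.** Section 3.2 of the Final Protocol gives one secondary outcome, the difference between arms in how anxious patients say they are. The measure is described as a "single question adapted from the Emotional Distress-Anxiety Short Form 4a scale on day 0, 7, and 14 after enrolment in COVID Watch". Section 3.3 places "health care utilization including outpatient, emergency department, inpatient, and ICU care" among the exploratory outcomes.

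The Final Statistical Analysis Plan (section E) does not mention anxiety, the survey item or days 0, 7 and 14. Its rules for secondary outcomes are general: "The researchers also compared continuous secondary outcomes including mean number of outpatient visits, emergency department encounters, and hospitalizations using t-tests", and "The researchers compared categorical secondary outcomes using Fisher's Exact test". It says covariate adjustment was not thought necessary because the arms were well balanced on sociodemographic and clinical characteristics. The mixed model carried over from the original SAP is for Days Alive and Out of Hospital (DAOH) only, and its covariates do not include a day-0 anxiety score.

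On missing data the SAP says: "The researchers will record and report all reasons for dropout and missing data, and account for all patients in reports". The only hint that a baseline survey exists is in the data-security text of Protocol 9.5.1: "Study and survey data collected during the baseline and subsequent visits will be kept electronically secure".

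**The concern.** The SAP gives its protocol-defined secondary outcome no analysis of its own. The generic rule does not say how the item is scored, and therefore whether the t-test or Fisher's test applies. It does not say how days 7 and 14 are read together, or what day 0 is for. Read with Protocol 3.2, it most naturally means three separate unadjusted comparisons, one of them at day 0.

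Day 0 is better used as a baseline. A between-arm difference there says nothing about using a device that is delivered later. The same score as a covariate would sharpen the comparisons at days 7 and 14 at no extra cost in data. At stake are the precision and clarity of the answer to the protocol's one secondary question.

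The tier label is a separate and smaller matter: utilisation appears more central in the SAP than the protocol makes it.

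**Working it through.** **No plan figure to reproduce.** The documents give no SD, effect size, power or sample size for anxiety. What can be checked is the text, and the precision of the alternative under stated assumptions.

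**Text, side by side.**

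| Item | Final Protocol | Final SAP |
|---|---|---|
| Anxiety item | Sole secondary outcome (3.2) | Not named |
| Days 0, 7, 14 | Stated (3.2) | Not mentioned |
| Use of day 0 | Listed as an assessment day | None stated |
| Outpatient, ED and inpatient use | Exploratory (3.3) | Called secondary |

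Neither summary of amendments (sections C and F) records a change of tier for utilisation.

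**Precision at one follow-up day.** Assumptions, none of them in the documents: numeric scoring, a linear model, equal SDs at day 0 and follow-up, and a day-0 to follow-up correlation r of 0.2, 0.4 or 0.6.

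The variance of the adjusted arm difference, relative to an unadjusted t-test at that day, is 1 − r². The equivalent gain in respondents is 1/(1 − r²).

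- r = 0.2: 1 − 0.04 = 0.96; 1/0.96 = 1.04, about 4% more respondents.
- r = 0.4: 1 − 0.16 = 0.84; 1/0.84 = 1.19, about 19% more.
- r = 0.6: 1 − 0.36 = 0.64; 1/0.64 = 1.56, about 56% more.

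**As detectable differences.** Take the SAP's minimum of 1078 patients, assume a 1:1 split (539 per arm), 80% power and two-sided 0.05. The detectable difference in SD units is (1.960 + 0.842) × √(2V/n), where V is the relative variance (1 for the t-test).

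| Respondents per arm | Unadjusted | r = 0.2 | r = 0.4 | r = 0.6 |
|---|---|---|---|---|
| 539 (all reply) | 0.171 | 0.167 | 0.156 | 0.137 |
| 270 (about half reply) | 0.241 | 0.236 | 0.221 | 0.193 |

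At the low end the gain is slight (0.171 against 0.167 SD); at the high end it is substantial. These figures are for one follow-up day. The gain for an arm effect averaged over days 7 and 14 also depends on the correlation between those days and is not quantified here.

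**Timing of day 0.** Adjustment is safe only if the score cannot have been affected by assignment. Protocol 8.2 lists no survey step. In step 3 the coordinator receives the arm assignments in a report of new enrollees, with two-hourly intervals given as an example. In step 4 "The RC alerts patients randomized to COVID Watch + Pulse Oximetry via phone call and/or text message", before the device arrives. The alert could therefore fall on day 0, before or after the anxiety reply. A reply given before delivery of the device is not necessarily a reply given before the patient knows the assignment.

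**The case against.** The strongest reply is that the outcome does have a method. The SAP's list of continuous secondary outcomes is introduced as examples, so the t-test and Fisher rules can cover the anxiety item. That stands. A reader might infer that the SAP plans no analysis of anxiety, and this goes too far: the rule is generic and unadjusted, but it exists and it is valid.

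Several stronger readings are tempting and lack support:

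- **Change from day 0.** A reader might take the t-test rule to allow a change-score analysis and measure the benefit of adjustment against that. Neither document mentions a change score, so the fair comparator is the single-day t-test.
- **Inflated error.** The 0.05 cut-off "was considered statistically significant in the primary analyses", so a reader might infer uncontrolled testing at days 7 and 14. But the next sentence turns to subgroups, and the contrast may simply be main against subgroup analyses. The SAP makes no family-wise claim for secondary outcomes. Naming one contrast is for clarity; it does not repair a broken guarantee.
- **Utilisation promoted after results were seen.** The documents do not show this. Section F says that the SAP modifications preceded outcome ascertainment, and the label may only be loose wording.

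Two further objections limit the point. The precision figures do not apply to Fisher's test if the item is treated as categorical. And day 0 is not established as a clean baseline, since the only mention of a baseline survey is in a data-security section. Both stand, and they make the recommendation conditional. The general commitment on missing data also covers part of what is asked for in reporting replies.

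**Conclusion.** The point holds as a minor, cheap improvement. The final SAP omits by name the protocol's only secondary outcome. The rule that applies by default leaves day 0 as one more unadjusted comparison, although it could serve as a baseline.

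At one follow-up day, adjusting for it is worth about 4%, 19% or 56% more respondents than the single-day t-test at correlations of 0.2, 0.4 and 0.6. This rests on numeric scoring, equal SDs and those assumed correlations. The benefit can be claimed only if day 0 precedes the alert to the oximetry arm, which the documents leave open.

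The tier mismatch for utilisation is plain on the current text and needs only a label or an explanation. The primary conclusion on DAOH is unaffected.

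**What to change.** **Anxiety.** Name the item and its scoring in the SAP, with a matching clarification of Protocol 3.2.

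- Compare arms at days 7 and 14 in one linear or ordinal repeated-measures model, with arm, day, arm-by-day and the day-0 score as covariate. Report day 0 descriptively.
- Make one contrast the secondary test, for example the arm effect averaged over both days, and show each day's estimate with its interval.
- Keep patients with no day-0 reply through a stated rule, such as a missing-baseline indicator. Include everyone with at least one follow-up reply, and report replies by arm and day.
- Adjust only if day 0 is collected before the oximetry arm is alerted. Otherwise keep the unadjusted comparison at days 7 and 14 as main.
- Label the adjusted result post hoc if it is added after outcomes are known. The SAP's analysis paragraph is partly in the past tense, so this may apply.

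**Utilisation.** Label it exploratory as in Protocol 3.3, or record the change of tier with its date and reason.

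**Cost.** One extra model, some wording and a check of when the day-0 item was sent; no new data, because the item is already planned. The model assumes that non-response at days 7 and 14 is explained by observed data, and the report should say so.

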### C. Summary of Amendments and Clarifications to Protocol

There were four modifications to the protocol. First, the researchers corrected the care escalation algorithm based on peripheral oxygenation saturation (SpO2) levels to more accurately reflect the original design and operating procedures of the COVID Watch + Pulse Oximetry program. Patients with a decrease in SpO2 by 3 or more percentage points to a level below 95% or with a reading below an absolute value of 90% triggered a care escalation alert to COVID Watch telemedicine clinician team.

Second, prior to randomizing the first participant, the researchers updated study eligibility criteria to include hospitalized patients who were initiated on COVID Watch as part of routine discharge care and exclude any patient already participating in an alternate monitoring program. The rationale for this change was that this design enabled the comprehensive capture of all patients initiated on COVID Watch and more accurately reflect the COVID Watch program's standard operating procedures.

Third, the researchers simplified the patient survey emotional distress and anxiety measure. This modification was also performed prior to randomizing the first patient. The rationale for this change was based on the feedback the researchers received from the community and patient stakeholder advisory committee.

Lastly, the researchers increased the sample size. The rationale for this change was due to a lower-than-expected COVID positivity rate and standard deviation in Days Alive Out of Hospital (DAOH) based on baseline COVID Watch program data through November 30, 2020.

Protocol Version	Amendment or Clarification	Dates
Final	Sample size was increased based on analysis of baseline data prior to trial (see amendment to statistical analysis plan)	12/17/20
	Patient survey emotional distress and anxiety measure was simplified to a single-item anxiety measure	11/02/20
	Eligibility criteria were updated to include hospitalized patients who were initiated on COVID Watch as part of routine discharge care and exclude any patient already participating in an alternate home monitoring program	11/02/20
	Care escalation algorithm based on peripheral oxygenation saturation (SpO 2 ) corrected to reflect original COVID Watch + Pulse Oximetry program design and operation	11/02/20

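### The final SAP names no method for ordered survey answers; if the single anxiety item has three or more levels and falls under the Fisher's exact rule, its order is ignored and power against a consistent shift is lost

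*Combined protocol and SAP*

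**What the plan says.** Section E (Final Statistical Analysis Plan) gives two rules for outcomes other than DAOH:

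- Continuous: "The researchers also compared continuous secondary outcomes including mean number of outpatient visits, emergency department encounters, and hospitalizations using t-tests".
- Categorical: "The researchers compared categorical secondary outcomes using Fisher's Exact test".

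It mentions no ordinal test or model, and no effect measure or confidence interval for categorical outcomes. The text carried over from the original SAP specifies linear mixed models for DAOH only.

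The final protocol's section 3.2 has one secondary outcome: "self-reported anxiety on a single question adapted from the Emotional Distress-Anxiety Short Form 4a scale on day 0, 7, and 14" after enrolment. Section C confirms the change: "Patient survey emotional distress and anxiety measure was simplified to a single-item anxiety measure". Section 3.3 lists, as exploratory, "self-perceptions of feeling safe at managing illness".

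Nowhere do the documents state the answer levels of either survey item, whether it is scored, collapsed or kept in categories, which day is compared, or how the day-0 answer is used.

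**The concern.** A question about how anxious or how safe a patient feels is commonly answered on a graded scale, and the clinical question is directional: does the device raise or lower anxiety? On a table of two arms by k levels, Fisher's exact test treats the levels as labels. Shuffle the levels and the p-value does not change. The test therefore spreads its sensitivity over k−1 degrees of freedom instead of aiming at a shift up or down.

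At stake is the only outcome the protocol designates as secondary. A real but moderate shift in anxiety would be more likely to be reported as no difference. With three or more levels, a significant p-value would not by itself summarise which way, or how far, the arms differ.

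**Working it through.** **Inputs.** The documents give no power, effect size, answer distribution or response rate for any survey item, so there is no plan figure to reproduce here. The stated sizing is for DAOH only ("204 Black or Latino patients in each arm to achieve 90% power to detect a mean difference of 1 DOAH"; total 1078). Everything below rests on assumptions:

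- Two-sided alpha 0.05. Section E makes all tests two-sided but ties 0.05 to the primary analyses.
- 1:1 allocation, which is not stated: 1078/2 = 539 per arm.
- 3, 4 or 5 ordered levels.
- A proportional-odds shift, that is, one common odds ratio (OR) across all cut-points.

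**Step 1: cost of the extra degrees of freedom.** Take a shift that a 1-df ordered test detects with 80% power. Its noncentrality is λ = (1.960 + 0.842)² = 7.85. Approximating Fisher's test on k levels by a chi-square test with k−1 df and the same λ, power = P(χ²(k−1, λ) > c), where c is the central 5% critical value:

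| Levels | df | c | Power | Loss from 80% |
|---|---|---|---|---|
| 2 | 1 | 3.841 | 80.0% | 0 |
| 3 | 2 | 5.991 | 70.9% | 9.1 points |
| 4 | 3 | 7.815 | 64.5% | 15.5 points |
| 5 | 4 | 9.488 | 59.5% | 20.5 points |

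At other ordered-test powers, the losses for 3, 4 and 5 levels are:

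- 50%: 9.9, 15.5 and 19.2 points
- 90%: 6.5, 11.6 and 16.0 points
- 99%: 1.3, 2.7 and 4.2 points

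**Step 2: simulation with the exact test.** Control proportions were (.5, .3, .2), (.35, .3, .2, .15) and (.3, .25, .25, .15, .05), the other arm was shifted by OR 1.4, and there were 1,500 trials per cell. Respondents were 270 or 430 per arm, about 50% and 80% of 539. Power, Wilcoxon versus Fisher:

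| Levels | 270 per arm | 430 per arm |
|---|---|---|
| 3 | 53% vs 43% | 74% vs 64% |
| 4 | 58% vs 39% | 77% vs 61% |
| 5 | 59% vs 38% | 78% vs 56% |

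The losses are 10, 19 and 21 points at 270 per arm, and 10, 16 and 22 at 430. A t-test on scores 0 to k−1 came within about 2 points of Wilcoxon.

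**Step 3: how far the loss moves.** A wider grid (OR 1.3 to 1.75; 204, 350 or 539 per arm; several answer distributions; 600 trials per cell; simulation error about 2–3 points) gave losses from about 0.5 to 24 points. The smallest came where both tests were nearly certain to reject. For example, with 5 skewed levels, 539 per arm and OR 1.75, power was 99.5% vs 98.3%.

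**Step 4: differences that are not a shift.** With 5 equally likely control answers, 350 per arm and a non-monotone difference, Fisher was far stronger:

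- Other arm (.26, .17, .14, .17, .26): Fisher 75%, Wilcoxon 4%
- Other arm (.14, .20, .26, .26, .14): Fisher 85%, Wilcoxon 10%
- Other arm (.20, .20, .20, .30, .10): Fisher 96%, Wilcoxon 16%

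**Step 5: collapsing to two categories.** On the Step 3 grid, cutting the scale and applying a 2×2 Fisher test lost about 0–18 points against Wilcoxon on the full scale. That loss comes mainly from the cut.

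**The case against.** The strongest objection is that the premise is not in the documents. Neither survey item is said to have three or more answers, and neither is assigned to Fisher's test. Because the question is adapted from the scale, its answer format is left open. The t-test list is also open, since it is introduced by the word including, and it already treats small counts as continuous, so a scored anxiety item could fall under it. Under two of the three possible readings (a binary item, or a scored one) there is no loss. Moreover, Fisher's test is a sound choice for binary outcomes such as 30-day mortality. The feeling-safe item is labelled exploratory, whereas the Fisher sentence speaks of secondary outcomes.

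Most of this stands, and it makes the point conditional. It does not remove it: the SAP does not say which reading is meant, and only an inherently two-answer item is handled properly by the Fisher rule as written. The exploratory label does not settle the feeling-safe item either, because section E applies the word secondary to utilisation outcomes that section 3.3 calls exploratory.

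A reader might infer that the plan fixes a loss of some 7 to 22 points, or that its categorical comparisons can show no direction. The documents support neither. Any such range depends on assumed levels, distribution, effect and response, and Steps 3 and 4 show it can shrink to almost nothing or reverse. Direction can be read from the proportions by arm, and a 2×2 table yields an odds ratio. The missing confidence interval is a general reporting silence, since section E specifies none for the t-tests either.

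**Conclusion.** The point holds in conditional form. The final SAP names no method for ordered outcomes, although its protocol's single secondary outcome is one question adapted from an anxiety scale. If that item, or the feeling-safe item, has three or more ordered answers and is treated as categorical, Fisher's test ignores the order. At 80% ordered-test power the loss against a consistent shift is then about 9, 16 or 21 points for 3, 4 or 5 levels.

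That size assumes a common shift across levels and two-sided alpha 0.05. It falls to about 1–4 points at 99% power and to zero if the item is binary; a scored and t-tested item also escapes it. The sign turns for some non-monotone differences. It should not be read as evidence that the trial's anxiety result was in fact analysed by Fisher's test; the documents do not say. The issue is confined to secondary and exploratory survey outcomes.

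**What to change.** In section E:

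- State the answer levels of the anxiety and feeling-safe items.
- Limit Fisher's exact test to binary or unordered outcomes.
- Analyse ordered survey items on all answer levels with a proportional-odds model at one named time point (day 7 or day 14), adjusted for the day-0 answer where available. Report the common odds ratio for the device arm against COVID Watch alone with a 95% CI.
- Use the Wilcoxon rank-sum test as a check, and do not collapse levels for the main comparison.

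Before adjusting, confirm that the day-0 answer is a true baseline. Section 8.2 has the coordinator tell device-arm patients that a device is coming, and the documents do not say whether the day-0 question comes first.

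The cost is a few sentences of SAP text and standard routines in R, which section E already names; no new data or patients are needed. The small downsides are a check of the proportional-odds assumption and less power for non-monotone differences.
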